1.2.2 UNCOMMON SIDE EFFECTS

Anaemia; encephalopathy; oedema; thrombocytopenia; weight increase.

1.2.3 RARE SIDE EFFECTS

Gynaecomastia; haemolytic anaemia; idiopathic intracranial hypertension; menstrual disorder; multifocal motor neuropathy; muscle weakness; myopathy; pancreatitis.

1.2.4 Drug interactions

Investigators should check for any relevant drug interactions in the Ciclosporin SmPC. Contraindicated medications include products containing *Hypericum perforatum* (St John's Wort) and medicines that are substrates for the multidrug efflux transporter P-glycoprotein (P-gp) or the organic anion transporter proteins (OATP) and for which elevated plasma concentrations are associated with serious and/or life-threatening events, e.g. bosentan, dabigatran etexilate and aliskiren (Investigators are advised to check the most recent SmPC for a more comprehensive list of medications that utilise these pathways).

1.3 SELECTION OF PARTICIPANTS

1.3.1 PARTICIPANT CORE INCLUSION AND EXCLUSION CRITERIA

To be eligible for randomisation, all participants must fulfil the core inclusion criteria and none of the exclusion criteria stated in section 5.3 of the main protocol in addition to the arm-specific criteria below.

Please note, as long as a participant is eligible to take ciclosporin (control arm) and at least one of the other trial treatments they can be randomised (i.e. they can meet exclusion criteria for one or more of the other treatments and still be randomised). If they fail to respond at 6 months, a pre-defined treatment switch (as per protocol) may or may not be possible depending on whether they still meet exclusion criteria for the relevant switch option. If the switch is not possible, they would be withdrawn from the trial at that stage.

1.3.2 CICLOSPORIN-SPECIFIC EXCLUSION CRITERIA

In addition to the core inclusion and exclusion criteria documented in the main protocol, the following arm-specific exclusion criteria apply for the ciclosporin arm.

1. Any contraindication to ciclosporin according to standard clinical care and/or the opinion of the investigator.

1.4 TREATMENT AND MONITORING OF PARTICIPANTS

1.4.1 PRODUCT INFORMATION

Dose: 3mg/kg orally daily increasing to 5mg/kg after 3 months if required (joint patient/investigator decision, as per standard practice). A dose reduction is permitted at any point and will be

documented in the participants medical notes/Source Data Worksheets and CRF. Dosing is to be calculated per body weight, not lean body weight.

Description of product: Ciclosporin 25mg, 50mg, 100mg capsules and 100mg/ml solution (for patients who are unable to swallow capsules or require solution for another reason). Any brand can be used. Ciclosporin must be prescribed and dispensed by brand name (MHRA/CHM advice). Where patients are stabilised on one brand and then switch to another brand (e.g. supply issues with contracted brand), close monitoring of the patient would be required in accordance with standard practice.

Packaging: Commercial/licenced packaging.

Prescription: Trial-specific prescription. Prescription template to be provided by sponsor..

Source of product: Hospital stock. No reimbursement from the Sponsor.

Storage: Store in accordance with the storage conditions outlined in the relevant SmPC. Store in the original package. In the event of a temperature excursion, manage according to local pharmacy practice.

Labelling: Attach a dispensing label in addition to a Sponsor label. Refer to the pharmacy manual for further details.

Accountability: The pharmacy clinical trials team must maintain accurate accountability records including, but not limited to, the number of packs/capsules received, the number of packs/capsules dispensed to which participant, the number of unused packs/capsules in quarantine or destroyed, as well as a record of the batch number and expiry date. It must be clearly documented in the medical notes and CRF when a prescription is issued. There will be no patient diaries, consistent with the pragmatic trial design and real world practice. Adherence should be discussed at each trial visit. A record of study drug returns is not required. Patients should be advised to take any medication that is no longer needed to a pharmacy (community/hospital) for disposal.

1.4.2 SAFETY VISITS AND MONITORING REQUIREMENTS

Timing of post-randomisation safety tests (bloods, urine, blood pressure and safety assessment) are shown in the main protocol schedule of events (Table 1, section 2 Trial Design), and in the drug-specific schedule of events at the beginning of each drug-specific appendix. Further details, including the exact laboratory tests required, are provided below.

1.4.2.1 SAFETY VISITS (ADDITIONAL TO MAIN TRIAL VISITS)

All participants randomised to ciclosporin will be followed up for safety at week 2 with additional visits at weeks 6 and 8. In addition, if their dose is increased at 3 months, they will be seen at weeks 15 and 17. In the event of dose reduction, additional safety assessments should be arranged at the discretion of the investigator.

1.4.2.2 SAFETY BLOOD PRESSURE READINGS

Safety assessment blood pressure readings will be measured at weeks 2, 4, 6, 8, 12, 24, 39 and 52 for those on ciclosporin. For those who dose increment on ciclosporin at month 3 additional blood pressure measurements will be taken at weeks 15 and 17 (see schedule of events, main protocol Section 2). Blood pressure should be measured in an upright position after the participant has been rested for five minutes

1.4.2.3 SAFETY BLOODS

The following safety bloods will be performed at weeks 2, 4, 6, 8, 13, 26, 39 and 52. For those who dose increment on ciclosporin at month 3 additional safety bloods will be performed at weeks 15 and 17 (see schedule of events, main protocol Section 2).

HAEMATOLOGY Haemoglobin Haematocrit Total and differential leukocyte count Red blood cell count Platelet count BIOCHEMISTRY Creatinine Potassium Liver function tests (LFTs) *Lipids *Urate

*screening and at months 3, 6, 9 and 12 only

1.4.2.4 URINALYSIS (BASELINE, MONTHS 1,3,6,9,12)

Urine protein:creatinine ratio will be performed at months 1,3,6,9,12.

1.4.3 MANAGING TOXICITY WITH CICLOSPORIN

Ciclosporin is licensed for use in this study population (adults with moderate to severe eczema). Investigators should refer to the summary of product characteristics in the event of toxicity.

Further British Association of Dermatologists drug related guidance for the safe and effective prescribing of ciclosporin can be found here:

Ciclosporin: https://onlinelibrary.wiley.com/doi/epdf/10.1111/bjd.17587

1.4.4 EVALUATING AE'S AND SAE'S – ASSESSMENT OF EXPECTEDNESS

Section 4.8 of the following SmPC's form the RSI for ciclosporin for this trial: Neoral Oral Solution (dated 15/09/2023); Neoral Soft Gelatin Capsules (dated 15/09/2023). These can be found in investigator site files (SmPC & Safety Alert Updates).

1.5 **References**

- 2. Goujon C, Viguier M, Staumont-Salle D, Bernier C, Guillet G, Lahfa M, Ferrier Le Bouedec MC, Cambazard F, Bottigioli D, Grande S, Dahel K, Bérard F, Rabilloud M, Mercier C, Nicolas JF.

Methotrexate Versus Cyclosporine in Adults with Moderate-to-Severe Atopic Dermatitis: A Phase III Randomized Noninferiority Trial. J Allergy Clin Immunol Pract. 2018;6:562-9 e3.

APPENDIX 2 DRUG-SPECIFIC INFORMATION: METHOTREXATE

TRIAL PARTICIPANT FLOW AND SCHEDULE OF EVENTS: METHOTREXATE

Version 2.1 29/01/2025

METHOTREXATE SCHEDULE OF EVENTS															
Event / form	Screening	Baseline ^A	Week 2 Safety Visit	Week 4 (Month 1)	Week 13 (Month 3)	Week 15 Safety Visit ⁸	Week 17 Safety Visit ⁸	PRIMARY OUTCOME Week 26 (Month 6)	Week 28 ^c Safety Visit	Week 30 Safety Visit ^c	Week 39 (Month 9)	Week 41 Safety	Week 43 Safety Visit ^D	Week 52 (Month 12) End of Study Visit	Ongoing
Informed Consent	Х														
Registration Form	Х														
Eligibility (confirmation only at baseline)	х	х													
Medical History and demographics	х														
Skin photography (optional)		Х						Х							
Randomisation Form (after all		v													
baseline data collected)		X													
Status Form				Х	Х			Х			Х			Х	
Physical examination*	Х	Х		Х	Х			Х			Х			Х	
Blood pressure	Х	Х													
Urinalysis	Х														
Pregnancy test*		Х						X++							
Eczema Area and Severity															
Index (EASI)		X		X	X			Х			Х			Х	
BLINDED ASSESSOR															
Investigator Global		v		v	v			v			v			v	
		×		~	×			×			X			~	
Detient Orientated Forema															
Measure (POEM)		X		Х	Х			Х			Х			Х	
Peak pruritus numerical		х		х	х			х			х			х	
rating scale (NRS)		~		V	v			X			v				
Eczema control (RECAP)		Х		X	Х			X			X			X	
Patient global assessment (PtGA)		х		х	Х			Х			Х			Х	
Dermatology Life Quality Index (DLQI)		х		х	х			х			Х			х	
EQ-5D-5L		Х			Х			Х			Х			Х	
PHQ-9		Х						Х						Х	
GAD-7		Х						Х						Х	
Resource use		Х			Х			Х			Х			Х	
Adherence check (VAS) &					v			v			>			v	
Tolerability					^			^			^			^	
Participant Online Surveys		Х												Х	
Dispense medication		Х			Х			Х			Х				
Screening blood tests (+DNA	x														
for filaggrin status, optional)	^														
Safety Blood Tests (can be		x	x	x	x	x	х	х	х	х	х	x	х	х	
remote)			~	~	~		~			~	~	~	~		
Safety assessment (can be										Х					
remote)""	 		 		 	 									
Methotrexate polyglutamate				х	Х			х							
Sample	 		 		 	 									
review								Х							
Study medication dose					v						v				
increment review											X				
Concomitant Medications Log															Χ
Topical treatments		Х		Х	Х			Х							
Adverse Events Log															Χ
Withdrawal Form															Χ
* Physical examination (according to routine clinical care) required at screening and baseline, extent of physical exam during follow up as															

deemed appropriate by investigator

** Only for those who switched treatment to methotrexate at 6 months

+ Women of childbearing potential only. Urine test

++ Repeat pregnancy test at 6 months for patients changing treatment from dupilumab or abrocitinib to methotrexate at 6 months

A: Baseline safety bloods for all treatments, at investigator discretion based upon timing of screening bloods

B: Week 15 & 17 safety bloods if methotrexate dose increased at week 13 $\,$

C: Week 28 & 30 safety bloods if switched to methotrexate at 6 months

D: Week 41 & 43 safety bloods check for patients who switched to methotrexate and dose increased only

Please note: if IMP is switched at 6 months, the schedule of events for the second IMP must be followed for the second 6 months of the trial.

CONTENTS

1 MET	HOTREXATE-SPECIFIC INFORMATION	84
1.1	BACKGROUND	
1.1.1	1 Background and mechanism	
1.1.2	2 Rationale for use of methotrexate	
1.1.3	3 Methotrexate dose justification	
1.1.4	Rationale for 6 month switch option from methotrexate (dupilumab)	
1.2	METHOTREXATE TOXICITY AND SAFETY	
1.2.1	1 Common side effects	
1.2.2	2 Uncommon side effects	
1.2.3	3 Rare side effects	
1.2.4	4 Drug interactions	
1.2.5	5 Post-treatment contraception requirements	
1.3	SELECTION OF PARTICIPANTS	
1.3.1	Participant core inclusion and exclusion criteria	
1.3.2	2 Methotrexate-specific exclusion criteria	
1.4	TREATMENT AND MONITORING OF PARTICIPANTS	
1.4.1	1 Product information	
1.4.2	2 Auxillary medicinal product: Folic acid	
1.4.3	3 Safety visits and monitoring requirements	
1.	4.3.1 Safety visits (in addition to main trial visits)	87
1.	4.3.2 Safety bloods	87
1.	4.3.3 Urine pregnancy test	87
1.4.4	4 Methotrexate polyglutamate level (months 1,3,6)	
1.4.5	5 Managing toxicity with methotrexate	
1.4.6	5 Evaluating AE's and SAE's – assessment of expectedness	
1.5	REFERENCES	

1 METHOTREXATE-SPECIFIC INFORMATION

1.1 BACKGROUND

1.1.1 BACKGROUND AND MECHANISM

Methotrexate is an antimetabolite (used as a chemotherapeutic agent since the early 1950s) that has immunomodulatory and anti-inflammatory effects. This is in part via the inhibition of folate-dependent enzymes which in turn suppresses transmethylation reactions and purine and pyrimidine synthesis which are required for effective lymphocyte function, for example. Further potentially relevant mechanisms include inhibiting the accumulation of polyamines (which contribute to inflammatory injury), increasing adenosine levels (affects cytokine secretion and the regulation of inflammation) and modulation of JAK/STAT and NF- κ B p38MAPK intra-signalling pathways¹.

1.1.2 RATIONALE FOR USE OF METHOTREXATE

Methotrexate is a key comparator as it is the most widely prescribed systemic treatment for adult eczema in the UK^7

1.1.3 METHOTREXATE DOSE JUSTIFICATION

Methotrexate will be initiated at 15mg weekly increasing to 20mg weekly if necessary, comparable to previous RCTs^{2,3}, real world practice based on published cohorts in the UK⁴ and France⁵, verbal consensus (feedback at UK DCTN steering group) and pre-trial UK wide clinician survey results (median starting dose 15 mg, 73% opting for the trial schedule chosen). Subcutaneous administration will optimise effectiveness (poor oral bioavailability in 20%, saturable absorption > 15mg weekly^{6,7}), improve tolerability, and is increasingly adopted in routine UK practice (feedback at UK DCTN steering group).

1.1.4 RATIONALE FOR 6 MONTH SWITCH OPTION FROM METHOTREXATE (DUPILUMAB)

For those participants on methotrexate who do not meet response criteria to continue at 6 months they can switch to dupilumab. Dupilumab was chosen as the switch option to most closely mirror clinical practice (in line with NICE TA534).

1.2 METHOTREXATE TOXICITY AND SAFETY

Administration of methotrexate for this study is not anticipated to induce any potential risk other than the known potential side effects listed below (please see SmPC accessible via the official Metoject website - https://metoject.co.uk). Methotrexate should not be used in men or women planning to conceive within 6 months, in pregnant women and in breast-feeding women.

1.2.1 COMMON SIDE EFFECTS

Anaemia; appetite decreased; diarrhoea; drowsiness; fatigue; gastrointestinal discomfort; headache; increased risk of infection; leucopenia; nausea; oral disorders; respiratory disorders; skin reactions; throat ulcer; thrombocytopenia; vomiting.

1.2.2 UNCOMMON SIDE EFFECTS

Agranulocytosis; alopecia; arthralgia; bone marrow disorders; chills; confusion; cystitis; depression; diabetes mellitus; dysuria; fever; gastrointestinal disorders; haemorrhage; healing impaired; hepatic disorders; myalgia; neoplasms; nephropathy; osteoporosis; photosensitivity reaction; rheumatoid arthritis aggravated; seizure; severe cutaneous adverse reactions (SCARs); vasculitis; vertigo; vulvovaginal disorders.

1.2.3 RARE SIDE EFFECTS

Azotaemia; brain oedema; cognitive impairment; conjunctivitis; cough; dyspnoea; eosinophilia; gynaecomastia; hypotension; immune deficiency; infertility; insomnia; lymphadenopathy; meningitis aseptic; menstrual disorder; mood altered; muscle weakness; nail discolouration; neutropenia; oligozoospermia; pain; pancreatitis; paresis; pericardial disorders; pericarditis; proteinuria; psychosis; radiation injuries; renal impairment; retinopathy; sensation abnormal; sepsis; sexual dysfunction; speech impairment; stress fracture; taste metallic; telangiectasia; tinnitus; visual impairment.

1.2.4 DRUG INTERACTIONS

Investigators should check for any relevant drug interactions in the methotrexate SmPC. Concurrent vaccination with live-vaccines is contra-indicated.

1.2.5 POST-TREATMENT CONTRACEPTION REQUIREMENTS

Both males and females need to continue effective contraception for a further 6 months after stopping methotrexate. Males cannot donate sperm whilst on methotrexate or within 6 months of stopping treatment.

1.3 SELECTION OF PARTICIPANTS

1.3.1 PARTICIPANT CORE INCLUSION AND EXCLUSION CRITERIA

To be eligible for randomisation, all participants must fulfil the core inclusion criteria and none of the exclusion criteria stated in section 5.3 of the main protocol in addition to the arm-specific criteria below.

Please note, as long as a participant is eligible to take ciclosporin (control arm) and at least one of the other trial treatments they can be randomised (i.e. they can meet exclusion criteria for one or more of the other treatments and still be randomised). If they fail to respond at 6 months, a pre-defined treatment switch (as per protocol) may or may not be possible depending on whether they still meet exclusion criteria for the relevant switch option. If the switch is not possible, they would be withdrawn from the trial at that stage.

1.3.2 METHOTREXATE-SPECIFIC EXCLUSION CRITERIA

In addition to the core inclusion and exclusion criteria documented in the main protocol, the following arm-specific exclusion criteria apply for the methotrexate arm.

- 1. Any contraindication to methotrexate according to standard clinical care and/or the opinion of the investigator.
- 2. Men and women planning conception within 6 months (cannot conceive for a minimum of 6months after stopping methotrexate and need to continue on effective contraception through that period).

1.4 **TREATMENT AND MONITORING OF PARTICIPANTS**

1.4.1 **PRODUCT INFORMATION**

Dose: Self-administered sub-cutaneous injection, 15mg once weekly, increasing to 20mg after 3 months if required (joint patient/investigator decision, as per standard practice). A dose reduction is

permitted at any point and will be documented in the participants medical notes/Source Data Worksheets and CRF.

Description of product: Metoject® 15mg and 20mg solution for injection in a pre-filled pen. Patients/carers must be trained on how to administer the product. In the unlikely event that Medac cannot supply Metoject® to sites, an alternative brand of methotrexate injection stocked at sites can be dispensed. Patients/carers must receive training on the new device, where applicable. A dose reduction is permitted at any point and will be documented in the participants medical notes/Source Data Worksheets and CRF.

Packaging: Commercial/licenced packaging.

Prescription: Trial-specific prescription. Prescription template to be provided by sponsor.

Source of product: Metoject® will be supplied free-of-charge to sites. If another brand is dispensed, hospital stock will be used, with no reimbursement from the Sponsor. Where another brand is dispensed, pharmacy staff should annotate the prescription with the brand supplied and notify the research team.

Storage: Store in accordance with the storage conditions outlined in the SmPC. Metoject® trial supplies must be stored separately to hospital stock and clearly labelled as trial stock. In the event of a temperature excursion, manage according to local pharmacy practice.

Labelling: Annex 13 (trial specific) labelling is required. Site pharmacy trial teams will be instructed to attach a dispensing label in addition to a Sponsor label which will cover the Annex 13 requirements. Refer to the pharmacy manual for further details.

Accountability:

The pharmacy clinical trials team must maintain accurate accountability records for each strength, including, but not limited to, the number of packs received, the number of packs dispensed to which participant, the number of unused packs in quarantine or destroyed, as well as a record of the batch number and expiry date. It must be clearly documented in the medical notes and CRF when a prescription is issued. There will be no patient diaries, consistent with the pragmatic trial design and real world practice. Adherence should be discussed at each trial visit. A record of study drug returns is not required for the trial. Any unused medicinal product or waste material should be disposed of in accordance with local requirements or by the participant within a sharps bin provided as per routine clinical practice. After use, place the pre-filled pen into a puncture-resistant container and discard as required by local regulations.

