Sample Size:	536 (134 per group) Please note the number of participants will be updated for additional arms as required

Study Population:	Adults with moderate to severe eczema requiring systemic therapy.
Maximum Duration of Treatment of a Participant:	1 year
Version and Date of Final Protocol:	Version 2.1, 29/01/2025

Revision History

Protocol version	Description of changes from previous revision	Effective Date
Protocol Version 1.0	New protocol (submitted for combined approval)	08.02.2023
Protocol Version 1.1	Adherence VAS check at Month 1 visit removed; Addition of Nested Interview Study Data Flow (Appendix 4); Correction of Sponsor SAE reporting process; Minor wording amendments for clarity.	07.09.2023
Protocol Version 1.2	Addition of REC and ISRCTN numbers; Removal of [name] as a co-applicant; Footer formatting and paragraph spacing; Addition of Be Part of Research Volunteer Service to participant identification; Edit to participant schedule of events footnote A; Addition of participant surveys to schedule of events; Minor edits to drug specific study flow footnotes; Postcode and mobile number removed from pre-randomisation data collection; Section 13.3 amended to reflect updated sponsor phamacovigilance policy; Amended wording to clarify process around participant online surveys; Wording in long-term follow up section amended to accurately reflect A- STAR data sharing; Amended wording in section 21 to reflect change from 'BEACONomics' to 'Allied Mechanistic Study'; Removal of 'BEACONomics' from Appenix 2 Data Flow.	11.04.2024

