2 TRIAL DESIGN

This is a UK, multicentre, one year, assessor-blind, randomised controlled trial assessing systemic treatments in adults with moderate to severe eczema. Three mechanistic classes of drugs are being tested against a control (ciclosporin). Further treatments and arms may be added in future amendments.

Participants will be randomised in a 1:1:1:1 ratio. **During the first stage of the trial (months 1-6)**, **follow up will be face to face at 1, 3 and 6 months** for safety and effectiveness assessment (see Figure 2 for trial flow diagram and Table 1 for schedule of events). There are additional drug-specific safety only visits for some arms as shown in Table 1, Figure 2, and individual flow diagrams in drug specific Appendices 1-4, in line with routine care and national guidance. There is the **option to increase the treatment dose at 3 months for some arms if there has been an inadequate response** following which additional safety only visits may be required (see Table 1 schedule of events, Figure 2 trial flow diagram, and individual flow diagrams in drug specific appendices 1-4). Dose reduction will be permitted at any stage as clinically indicated and according to standard clinical practice. Safety only visits (when no additional effectiveness measure is conducted) can be conducted in the community where deemed appropriate by the investigator (general practice). If participants attend study sites, contact with study staff should be minimised and staff will be trained to not provide additional support to minimise performance bias.

The primary outcome will be assessed at 6 months. Responders, defined as those achieving at least a 50% improvement in the objective EASI score (EASI50) and $a \ge 4$ point reduction in Dermatology Life Quality Index (DLQI) will continue the same therapy for a further 6 months (up to 1 year) if they are tolerating the treatment and are happy to continue (in line with NICE guidance (NICE TA534¹⁷)). Non-responders will switch therapy in a pre-determined way that mirrors real world practice (see Figure 2).

In the second stage of the trial (months 7-12) face to face safety and effectiveness assessments will be at 9 and 12 months. For those participants who have switched therapy there will be an additional telephone/ remote safety only visit (with bloods) at 7 months. Dependent upon

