5.3.2 EXCLUSION CRITERIA

- 1. Active dermatologic conditions that may confound the diagnosis of atopic eczema or interfere with assessment of treatment.
- 2. Prior exposure to any of the systemic therapies being investigated in the trial or those with a similar mechanism of action to the systemic therapies being investigated in the trial (see drug specific appendices for examples of excluded drugs and further information).
- 3. Receipt of any of the following:
 - a. Phototherapy (UVB TL01, UVB, PUVA, UVA1), tanning beds, oral or parenteral traditional Chinese medicine or oral systemic immunosuppressant/ immunomodulatory agent that can help eczema (including but not limited to prednisolone, azathioprine, mycophenolate mofetil, tacrolimus, Janus kinase (JAK) inhibitor or phosphodiesterase 4 inhibitor) within 4 weeks prior to randomisation.
 - b. Biologic therapy for eczema (including but not limited to amlitelimab, rocatinlimab and nemolizumab) within 3 months prior to randomisation.
 - c. Receipt of a cell-depleting agent (e.g. rituximab, alemtuzumab, cyclophosphamide, chlorambucil) for 6 months prior to randomisation or until lymphocyte count returns to normal (whichever is longer)
- 4. Any medical condition that, in the opinion of the investigator, may compromise the safety of the participant in the trial, interfere with evaluation of the IMP, or reduce the participant's ability to participate in the trial.
- 5. Receipt of live/ live attenuated vaccine 30 days prior to the baseline visit date or expected need of live / live attenuated vaccination during the trial.
- 6. Participating in another clinical trial.
- 7. Women of child-bearing potential (WOCBP*) at risk of pregnancy during the trial (i.e. sexually active women not on effective contraception **)
- 8. Women who are pregnant or breastfeeding.

* WOCBP defined as: fertile, following menarche and until becoming post-menopausal unless permanently sterile. Permanent sterilisation methods include hysterectomy, bilateral salpingectomy and bilateral oophorectomy. A postmenopausal state is defined as no menses for 12 months without an alternative medical cause.

**Effective methods of contraception include:

- combined (oestrogen and progestogen containing) hormonal contraception associated with inhibition of ovulation:
 - oral
 - intravaginal
 - transdermal
- progestogen-only hormonal contraception:
 - oral
 - injectable
 - implantable
- o intrauterine device (IUD)

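### The methotrexate exclusion looks 6 months ahead for planned conception from an unstated start, which conflicts with the protocol's own treatment and post-treatment periods for men (months 7-18) and for women (months 13-18)

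*Protocol*

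**What the plan says.** Appendix 2 section 1.3.2, criterion 2, excludes from the methotrexate arm "Men and women planning conception within 6 months". Its bracket adds that conception is barred for at least 6 months after the drug is stopped, and requires contraception over that later period. Appendix 2 section 1.2 repeats the horizon without the bracket: "Methotrexate should not be used in men or women planning to conceive within 6 months". Neither place says what the 6 months are counted from.

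The exposure and follow-on periods are set elsewhere. The Synopsis gives 1 year under "Maximum Duration of Treatment of a Participant". Section 2 says that responders "will continue the same therapy for a further 6 months (up to 1 year) if they are tolerating the treatment". Appendix 2 section 1.2.5 states: "Both males and females need to continue effective contraception for a further 6 months after stopping methotrexate".

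Participants who do not respond to dupilumab or abrocitinib can switch to methotrexate at month 6 (section 1.1.4 of Appendices 3 and 4). The switch drug's exclusions are checked again at that point (section 5.3.3; Appendix 2 section 1.3.1).

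Among the core criteria, exclusion 7 in section 5.3.2 removes "Women of child-bearing potential (WOCBP*) at risk of pregnancy during the trial" from every arm, with a gloss that describes sexually active women who are not using effective contraception. Section 6.3.3 records the conception plans of both sexes before randomisation and notes that men's plans matter for methotrexate.

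**The concern.** An eligibility window for planned conception should agree with the period in which the same document says conception must be avoided. Here the stated window is 6 months, while the avoidance period is the time on drug plus a further 6 months. On the natural reading, with the clock starting at screening or randomisation, a man who says he plans to conceive at month 9 is outside the window of criterion 2, and no other numbered criterion mentions men's plans. He could be allocated methotrexate although his stated plan conflicts with the restriction in the same appendix.

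The first stake is safety. The second is consistent application. Section 12.3 limits each comparison to participants with no contraindication to either drug, so sites that read the window differently would admit different people to the methotrexate-ciclosporin comparison. The third is exposure: a participant who keeps to such a plan must stop methotrexate early, possibly before the month-6 primary endpoint.

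**Working it through.** This is timeline arithmetic. No power or error-rate calculation is involved.

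Inputs:
- H, the look-ahead in the criterion: 6 months (Appendix 2 sections 1.3.2 and 1.2).
- T, the time on methotrexate: 12 months for a responder randomised to it (Synopsis; section 2); 6 months for a non-responder who leaves it at month 6; 6 months (month 6 to month 12) for a participant switched to it.
- W, the period after stopping: 6 months, both sexes (Appendix 2 section 1.2.5, and the bracket in 1.3.2).

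Formulas, counted from the start of methotrexate: restricted span R = T + W; uncovered = R - H.

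The plan's own figure first: R = 6 requires T = 0, since 0 + 6 = 6. The 6 months therefore match the restriction only if the clock starts when methotrexate stops.

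| Participant | T | W | R | R - H |
|---|---|---|---|---|
| Responder randomised to methotrexate | 12 | 6 | 18 | 12 |
| Non-responder who leaves it at month 6 | 6 | 6 | 12 | 6 |
| Switched to it at month 6, H re-applied at the switch | 6 | 6 | 12 from the switch (month 18 of the trial) | 6 |

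Now overlay core exclusion 7, which covers women to month 12:
- Responder on methotrexate: men are uncovered for months 7-18 (18 - 6 = 12 months) and women for months 13-18 (18 - 12 = 6 months).
- Non-responder who leaves at month 6: men are uncovered for months 7-12. For women the restriction ends with the trial period, so nothing remains.
- Switched at month 6: the re-applied 6 months reach month 12, so months 13-18 are uncovered for both sexes.

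The start of the clock matters in itself. Screening may be up to 12 weeks before randomisation (section 6.1.1), and medical history, which includes conception plans, is scheduled at screening only (Table 1). Six months (26 weeks) counted from the earliest screening date end 26 - 12 = 14 weeks after randomisation.

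Consequence for exposure: a plan for month m implies stopping by month m - 6. For month 9 that is 9 - 6 = month 3, before the primary endpoint at month 6.

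**The case against.** The strongest reply is that the wording is unclear and not wrong. The start is undefined, and the bracket in criterion 2 links the 6 months to the time after stopping; on that reading there is no gap. This stands in part: the defect is partly one of ambiguity. But section 1.2 of the same appendix repeats the horizon with no such bracket, and neither place fixes the start.

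A second reply is that other safeguards exist. Methotrexate exclusion 1 admits any contraindication in the investigator's opinion, with no time limit, and plans are recorded before randomisation. An investigator who hears of a month-9 plan therefore has grounds to close the arm. That also stands, but it leaves to discretion what a numbered criterion appears to settle with a shorter figure.

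A reader might go further in four ways that the protocol does not support:
- That anyone planning conception in months 7-18 passes eligibility. Core exclusion 7 reaches women during the trial. Months 7-12 are at most arguable for women, because the gloss is worded around current contraception and a woman who uses it now but plans to stop does not literally meet it.
- That men have no contraception duty. Criterion 2 names both sexes, and its bracket and section 1.2.5 impose the duty.
- That 18 months applies to everyone. It applies to those who stay on methotrexate to month 12; a non-responder who leaves at month 6 is restricted to month 12.
- That the primary comparison will be damaged by early stopping. No figure shows how many participants hold such plans, and those who stop drug are still followed (section 7.3) and analysed as randomised (section 12.3).

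**Conclusion.** The concern holds in a limited form. If the 6 months run from screening or randomisation, criterion 2 and the matching sentence in section 1.2 contradict the protocol's own treatment and post-treatment periods. Counted from randomisation, the explicit criteria leave uncovered up to 12 months for men (months 7-18) and up to 6 months for women (months 13-18). For participants switched to methotrexate, the re-check at month 6 uses the same horizon and falls 6 months short.

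This rests on three assumptions: the clock starts at screening or randomisation; treatment runs to a protocol decision point (month 6 or month 12); and core exclusion 7 is read by its main words, so that it covers women throughout the trial. It is a safety-relevant inconsistency in an eligibility rule. The number of participants affected cannot be estimated from the protocol.

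**What to change.** Reconcile Appendix 2 sections 1.2 and 1.3.2 with the Synopsis, section 2, core exclusion 7 in section 5.3.2, and Appendix 2 section 1.2.5. The amended criterion should state when its period starts, be consistent with the protocol's own treatment and post-treatment periods for both men and women, and say how it applies when exclusions are checked again at the month-6 switch. The length of the period is a clinical decision for the sponsor; none is proposed here.

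The cost is a wording amendment. Conception plans of both sexes are already recorded before randomisation (section 6.3.3); because that record is scheduled at screening only, the amendment should also say how plans are ascertained at the switch. The downside is small: methotrexate would be closed to a few more participants, who may still be randomised if eligible for ciclosporin and at least one other arm. A few dupilumab or abrocitinib non-responders might be unable to switch, and section 5.3.3 would then withdraw them at month 6.
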